3.3.5 Rationale for Treatment beyond Disease Progression per RECIST v1.1

Patients in either study cohort may continue treatment beyond disease progression per RECIST v1.1 for two reasons: possible pseudoprogression due to immunotherapy, or disease progression is limited to ≤ 3 intracranial lesions that may be controlled by SRT.

In studies of immunotherapeutic agents, complete response (CR), PR and stable disease (SD) have each been shown to occur after radiographic evidence of an apparent increase in tumour burden. This initial increase in tumour burden caused by immune-cell infiltration in the setting of a T cell response has been termed pseudoprogression ([Hales et al. 2010](#)). In single agent atezolizumab studies (Study PCD4989g – see Atezolizumab Investigator's Brochure), evidence of tumour growth followed by a response was observed in several tumour types. In addition, in some responding patients with radiographic evidence of progression, biopsies of new lesions or areas of new growth in existing lesions revealed infiltrating immune cells and no viable cancer cells. Because of the potential for a response after pseudoprogression, this study will allow treatment in either cohort to continue after apparent radiographic progression per RECIST v1.1, provided the benefit-risk ratio is judged to be favourable (see criteria in Section [3.1](#)).

The blood brain barrier limits drug delivery to intracranial disease sites ([Agarwala et al. 2000](#)). A probable result of this sequestration is that, while disease outcomes have improved with the introduction of new systemic agents (see Section [1.1](#)), intracranial disease progression despite stable or responding extracranial disease has become more common ([Soliman et al. 2015](#)). Though randomized studies evaluating systemic treatment with SRT are limited, the practice of managing brain lesions with SRT in patients whose extracranial disease is controlled by systemic treatment has become a common clinical practice. The value of this approach has been supported by multiple retrospective analyses in melanoma patients receiving SRT with immunotherapy and/or targeted agents ([Anderson et al. 2017](#); [Choong et al. 2017](#), [Ahmed et al. 2016](#); [Mathew et al. 2013](#); [Knisely et al. 2012](#)).

Study treatment will be discontinued in any study patient who continues treatment beyond disease progression per RECIST v1.1 if clinical deterioration because of disease progression occurs at any time or if persistent disease growth is confirmed on follow-up disease assessments performed approximately four weeks later (or sooner if indicated due to clinical progression). Notably, the disease status of patients who continued study treatment and underwent intracranial SRT will be determined by the investigator according to RECIST v1.1 modified by excluding any treated lesions from the sum of largest diameters from baseline onwards.

3.3.6 Rationale for Patient-Reported Outcome Assessments

The goal of cancer treatment is to increase survival and delay of tumour progression not at the expense of the patients' quality of life ([Peppercorn et al. 2011](#)). Melanoma has

Cobimetinib, atezolizumab, vemurafenib — F. Hoffmann-La Roche Ltd

one the highest percentage of brain metastases relative to other primary tumours. The role of immunotherapy in treatment of brain metastases is unknown because most trials exclude patients with active brain lesions ([Preusser et al. 2012](#), Section 1.1). Therefore, assessing the impact of treatment and disease burden on patients' HRQoL and activities of daily living provides a holistic view of how the full treatment profile impacts patients' lives.

The EORTC QLQ-C30, a generic cancer questionnaire that assesses commonly reported symptoms, functioning, and Global Health Status (GHS)/HRQoL; and the brain cancer module (QLQ-BN20) are validated instruments selected for this study to obtain patient-relevant information. Secondary efficacy PRO endpoints evaluated in this study will be based on changes detected in the QLQ-C30 or QLQ-BN20 symptoms subscale scores that are perceived by patients as clinically significant ([Osoba et al. 1998](#)). These data will therefore provide meaningful measures of patients' experience with melanoma treatment.

Assessment of the effects of combination treatment with cobimetinib and atezolizumab or with cobimetinib, atezolizumab and vemurafenib in relation to disease and treatment burden will allow oncologists to appropriately educate patients on the benefits and risks of treatment with these regimens.

3.3.7 Rationale for Biomarker Assessments

Melanoma is a heterogeneous disease driven by aberrations in cancer-related genes including BRAF and NRAS gene mutations. Differences in the genetic makeup of melanoma is likely to influence clinical response and changes in the genetic makeup give insights into potential mechanisms of acquired resistance. The aim is to characterize melanoma disease among patients, to better understand clinical responses, and to assess potential mechanisms of acquired resistance.

Tumour tissue obtained from study participants prior to study treatment initiation will be collected only if such samples are already available. It will be examined for the expression of PD-L1 protein. In addition, if sufficient tumour material is available, an analysis of cancer related genes (such as, but not limited to, BRAF and NRAS) may be performed using next-generation sequencing (NGS). The results will be analysed in relation to clinical response to identify those patients with a greater likelihood of benefiting from study treatment.

Factors in plasma hold important clues regarding the disease pathobiology of cancer patients and may serve as a surrogate for tumour tissue in cases where tissue is not easily accessible. An exploratory objective of this study is to assess biomarkers in plasma at baseline and at the time of relapse. Analysis of plasma may include the analysis of cancer related genes by performing NGS of circulating tumour DNA.

4. **MATERIALS AND METHODS**

4.1 **PATIENTS**

Approximately 60 patients with BRAF^{V600} mutation-positive melanoma patients with CNS metastases (Cohort 2) will be enrolled in this study. Enrollment has been discontinued into Cohort 1 (BRAF^{V600} wild-type cohort).

4.1.1 **Inclusion Criteria**

Patients must meet the following criteria for study entry.

Disease-specific criteria

- Histologically confirmed melanoma with radiologically confirmed brain metastases
- Documented BRAF^{V600} mutation status of melanoma tumour tissue using a validated genetic test.
- Measurable brain metastases defined as any lesion that can be accurately measured in at least one dimension as ≥ 0.5 cm by MRI. Patients who have received prior SRT or surgery for brain metastases must have untreated brain lesions that can be accurately measured in at least one dimension as ≥ 0.5 cm by MRI.
- Prior anti-cancer therapy for metastatic melanoma is allowed, with the following exceptions:
 - Prior BRAF or MEK inhibitors are not allowed in either the metastatic or adjuvant settings
 - Prior immunotherapy is not allowed. As an exception, for patients in Cohort 1 (BRAF^{V600} wild-type) prior immunotherapy is allowed in the adjuvant setting if completed ≥ 90 days prior to study treatment initiation. Examples of immunotherapy include, but are not limited to, nivolumab, pembrolizumab and ipilimumab.
 - Any anti-cancer therapy, including chemotherapy, hormonal therapy and radiotherapy, is prohibited within two weeks prior to initiation of study treatment
- Prior SRT or surgical therapy of ≤ 10 brain metastases is allowed but prior WBRT is not allowed.
- Adverse effects of all prior systemic or local treatment must have either returned to baseline or become stable and manageable prior to initiation of study treatment.

General criteria

- Willing and able to provide informed consent and have signed the study Informed Consent Form
- Age ≥ 18 years at time of signing Informed Consent Form
- Able to comply with the study protocol, in the investigator's judgment
- ECOG Performance Status ≤ 2
- Life expectancy of > 3 months

- Willing and able to complete health and quality of life questionnaires required by the protocol
- Adequate hematologic and end-organ function, defined using the following laboratory results obtained within 14 days prior to first dose of study treatment with the exception of amylase and lipase which may be obtained within 28 days prior to study treatment initiation:
 - Absolute neutrophil count $\geq 1.5 \times 10^9/L$ without granulocyte colony-stimulating factor support
 - White blood cell count $\geq 2.5 \times 10^9/L$
 - Lymphocyte count $\geq 0.5 \times 10^9/L$
 - Platelet count $\geq 100 \times 10^9/L$ without transfusion
 - Haemoglobin $\geq 90 \text{ g/L}$ without transfusion
 - Serum albumin $\geq 25 \text{ g/L}$
 - Total bilirubin $\leq 1.5 \times$ upper limit of normal (ULN)
 - Aspartate transaminase and ALT $\leq 2.0 \times$ ULN, or for patients with documented liver metastases, ≤ 5.0 ULN
 - *For patients assigned to Cohort 2 only:* Amylase and lipase $\leq 1.5 \times$ ULN
 - Alkaline phosphatase (ALP) $\leq 2.5 \times$ ULN or, for patients with documented liver or bone metastases ALP $\leq 5 \times$ ULN
 - Serum creatinine $\leq 1.5 \times$ ULN or creatinine clearance (CrCl) $\geq 40 \text{ mL/min}$ on the basis of measured CrCl from a 24-hour urine collection or Cockcroft-Gault glomerular filtration rate estimation as follows:
$$\text{CrCl} = \frac{(140 - \text{age}) \times (\text{weight in kg}) (\times 0.85 \text{ if female})}{72 \times (\text{serum creatinine in mg/dL})}$$
 - For patients not receiving therapeutic anticoagulation: international normalised ratio (INR) or activated partial thromboplastin time (aPTT) $\leq 1.5 \times$ ULN within 28 days prior to initiation of study treatment

For patients receiving therapeutic anticoagulation: stable anticoagulant regimen that does not include coumarin anticoagulants, stable INR and stable aPTT during the 28 days immediately preceding initiation of study treatment.
- Female patients of childbearing potential and male patients with partners of childbearing potential must agree to always use two effective forms of contraception including at least one method with a failure rate of $< 1\%$ per year during the course of this study and for at least six months after completion of study therapy.
 - Females of childbearing potential are defined as sexually mature women without prior oophorectomy or hysterectomy who have had menses within the last 12 months.
 - Females are not considered to be of childbearing potential if amenorrhoeic for > 12 months and follicle-stimulating hormone (FSH) level $\geq 40 \text{ IU/L}$. For

females who have been amenorrhoeic for \geq 2 years, the requirement for FSH measurement at screening will be waived.

- Examples of effective contraception methods with a failure rate of < 1% per year include bilateral tubal ligation and male surgical sterilization; hormonal contraceptives that inhibit ovulation; hormone-releasing intrauterine devices; and copper intrauterine devices. A reliable barrier method may be used as the second contraceptive method. Hormonal contraceptive methods must be supplemented by a barrier method. Please note that potential interactions between vemurafenib and hormonal contraceptives may decrease the effectiveness of hormonal contraceptives.
- Male patients who are surgically sterilized are required to use barrier methods of contraception.
- Female patients of childbearing potential must agree to refrain from donating eggs during the course of the study and for at least 5 months after their final dose of atezolizumab
- Male patients must agree to refrain from donating sperm during the course of the study and for at least six months after the last dose of cobimetinib

4.1.2 Exclusion Criteria

Patients who meet any of the following cancer-related or general criteria will be excluded from study entry:

Cancer-related criteria

- Ocular melanoma
- Leptomeningeal involvement
- Uncontrolled tumour-related pain

Patients requiring narcotic pain medication must be on a stable regimen at start of study treatment.

Symptomatic lesions amenable to palliative radiotherapy (e.g., bone metastases or metastases causing nerve impingement) should be treated prior to enrollment.

Patients should be recovered from the effects of radiation. There is no required minimum recovery period.

Asymptomatic metastatic lesions that would likely cause functional deficits or intractable pain with further growth (e.g., epidural metastasis that is not currently associated with spinal cord compression) should be considered for loco-regional therapy, if appropriate, prior to enrollment.

- Uncontrolled pleural effusion, pericardial effusion, or ascites requiring repeated drainage more than once every 28 days. Note: indwelling drainage catheters (e.g., PleurX[®]) are allowed.
- Prior WBRT treatment for CNS disease
- Increasing corticosteroid dose during the seven days prior to initiation of study treatment or current dexamethasone or equivalent dose of > 8 mg/day

- Prior treatment with a BRAF or MEK inhibitor
- Major surgical procedure other than for diagnosis within four weeks prior to initiation of study treatment, or anticipation of need for a major surgical procedure during the course of the study
- Known hypersensitivity to biopharmaceutical agents produced in Chinese hamster ovary cells or to any formulation component of cobimetinib or atezolizumab or, *for patients assigned to Cohort 2 only*, vemurafenib.
- *Patients assigned to Cohort 2 only:* Concomitant treatment with anticonvulsants other than gabapentin, vigabatrin and levetiracetam
- *Patients assigned to Cohort 2 only:* acetaminophen is prohibited within seven days prior to initiation of study treatment unless the patient has an absolute contraindication to the use of non-steroidal anti-inflammatory drugs (NSAIDs) or aspirin (i.e., severe allergy or reactive airway disease sensitive to NSAIDs or aspirin).
- Active malignancy (other than melanoma) or a prior malignancy within the past three years

Patients with completely resected basal cell carcinoma, cutaneous squamous cell carcinoma (cuSCC), cervical carcinoma *in situ*, breast carcinoma *in situ*, prostate cancer *in situ* or limited stage bladder cancer, and patients with isolated elevation in prostate-specific antigen in the absence of radiographic evidence of metastatic prostate cancer are eligible for the study.

General criteria

- Known risk factors for ocular toxicity, consisting of any of the following:
 - History of serous retinopathy
 - History of retinal vein occlusion (RVO)
 - Evidence of ongoing serous retinopathy or RVO at baseline
- History of clinically significant cardiac dysfunction, including the following:
 - Unstable angina or new-onset angina within three months prior to initiation of study treatment
 - Current symptomatic congestive heart failure, defined as New York Heart Association Class II or higher
 - Myocardial infarction within three months prior to initiation of study treatment
 - Unstable arrhythmia
 - Left ventricular ejection fraction below the institutional lower limit of normal or below 50%, whichever is lower
 - Poorly controlled hypertension, defined as sustained, uncontrolled, non-episodic baseline hypertension consistently above 159/99 mmHg despite optimal medical management
 - *For patients assigned to Cohort 2 only:* History of congenital long QT syndrome

- *For patients assigned to Cohort 2 only:* Mean (average of triplicate measurements) QTc interval corrected using Fridericia's method (QTcF) ≥ 480 ms at screening, or uncorrectable abnormalities in serum electrolytes (sodium, potassium, calcium, magnesium and phosphorus)
- Inability to swallow medications
- Malabsorption condition that would alter the absorption of orally administered medications
- Traumatic injury within two weeks prior to initiation of study treatment
- Prior allogeneic stem cell or solid organ transplantation
- Active or history of autoimmune disease or immune deficiency, including, but not limited to, myasthenia gravis, myositis, autoimmune hepatitis, systemic lupus erythematosus, rheumatoid arthritis, inflammatory bowel disease, anti-phospholipid antibody syndrome, Wegener granulomatosis, Sjögren syndrome, Guillain-Barré syndrome, or multiple sclerosis (see complete list in [Appendix 10](#)), with the following exceptions:
 - Patients with a history of autoimmune-related hypothyroidism who are on thyroid-replacement hormone are eligible for the study.
 - Patients with controlled Type 1 diabetes mellitus who are on an insulin regimen are eligible for the study.
 - Patients with eczema, psoriasis, lichen simplex chronicus, or vitiligo with dermatologic manifestations only (e.g., patients with psoriatic arthritis are excluded from the study) are eligible for the study provided all of following conditions are met:
 - Rash covering $< 10\%$ of body surface area
 - Well-controlled disease at baseline requiring only low-potency topical corticosteroids
 - No occurrence of acute exacerbations of the underlying condition requiring psoralen plus ultraviolet A radiation, methotrexate, retinoids, biologic agents, oral calcineurin inhibitors, or high-potency or oral corticosteroids within 12 months of study treatment initiation
- History of idiopathic pulmonary fibrosis, organizing pneumonia (e.g., bronchiolitis obliterans), drug-induced pneumonitis, or idiopathic pneumonitis, or evidence of active pneumonitis on screening chest computed tomography (CT) scan
History of radiation pneumonitis in the radiation field (fibrosis) is permitted.
- Uncontrolled diabetes or symptomatic hyperglycaemia
- Any Grade ≥ 3 haemorrhage or bleeding event within 28 days of study treatment initiation
- History of stroke, reversible ischemic neurological defect, or transient ischemic attack within six months prior to study treatment initiation
- Positive human immunodeficiency virus (HIV) test at screening

- Hepatitis B virus (HBV) infection (chronic or acute), defined as having a positive hepatitis B surface antigen (HBsAg) test at screening or a positive quantitative HBV DNA test.
If a patient has a negative HBsAg test and a positive total hepatitis B core antibody (HBcAb) test at screening, a quantitative HBV DNA test must be performed. If positive, the patient is not eligible.
- Patients receiving anti-viral therapy for HBV are not eligible for study enrollment.
- Active hepatitis C virus (HCV) infection, defined as having a positive HCV antibody test and a positive HCV RNA test at screening
- Active tuberculosis
- History of severe allergic, anaphylactic or other hypersensitivity reactions to chimeric or humanized antibodies or fusion proteins
- Severe infection within four weeks prior to initiation of study treatment, including, but not limited to, hospitalization for complications of infection, bacteraemia, or severe pneumonia, *or any active infection that, in the opinion of the investigator, could impact patient safety*
- Signs or symptoms of infection within two weeks prior to initiation of study treatment
- Any serious medical condition or abnormality in clinical laboratory tests that, in the investigator's judgment, precludes the patient's safe participation in, and completion of, the study
- Any psychological, familial, sociological, or geographical condition that may hamper compliance with the protocol and follow-up after treatment discontinuation
- Pregnancy, breastfeeding, or intention of becoming pregnant during the study. Women of childbearing potential must have a negative serum pregnancy test result within seven days prior to initiation of study treatment.
- Treatment with therapeutic oral or IV antibiotics within two weeks prior to initiation of study treatment
Patients receiving prophylactic antibiotics (e.g., to prevent a urinary tract infection or chronic obstructive pulmonary disease exacerbation) are eligible for the study.
- Administration of a live, attenuated vaccine within four weeks prior to initiation of study treatment or anticipation of need for such a vaccine during the study
- Treatment with systemic immunostimulatory agents (including, but not limited to, interferons, IL-2) within 28 days or 5 half-lives of the drug, whichever is shorter, prior to study treatment initiation
- Treatment with systemic immunosuppressive medications (including, but not limited to cyclophosphamide, azathioprine, methotrexate and thalidomide) within two weeks prior to study treatment initiation.
Patients who received mineralocorticoids (e.g., fludrocortisone), corticosteroids for chronic obstructive pulmonary disease (COPD) or asthma, or low-dose

corticosteroids for orthostatic hypotension or adrenal insufficiency are eligible for the study.

- Treatment with investigational drug within 28 days or 5 half-lives of the drug, whichever is longer, prior to initiation of study treatment
- *For patients to be assigned to Cohort 2 only:* anticipated use of any concomitant medication during or within seven days prior to initiation of study treatment that is known to cause QT prolongation
- Consumption of foods, supplements, or drugs that are strong or moderate CYP3A4 enzyme inducers or inhibitors at least seven days prior to initiation of study treatment.

These include St. John's wort or hyperforin (strong CYP3A4 enzyme inducer) and grapefruit juice (strong cytochrome P450 CYP3A4 enzyme inhibitor).

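### The CYP3A4 entry exclusion is worded *at least* seven days before first dose where *within* seven days is meant, so read literally it leaves Day -6 to Day -1 open

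*Protocol*

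**What the plan says.** Protocol 4.1.2 excludes a patient for taking anything classed as "strong or moderate CYP3A4 enzyme inducers or inhibitors at least seven days prior to initiation of study treatment", whether it is a food, a supplement or a drug. It gives St. John's wort (or hyperforin) and grapefruit juice as examples. The synopsis repeats the criterion in the same words, so neither statement corrects the other.

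The other seven-day criteria in 4.1.2 are worded differently:

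- Corticosteroids: "Increasing corticosteroid dose during the seven days prior to initiation of study treatment".
- Acetaminophen, Cohort 2: "acetaminophen is prohibited within seven days prior to initiation of study treatment".
- Pregnancy test: "negative serum pregnancy test result within seven days prior to initiation of study treatment".
- QT-prolonging drugs, Cohort 2, immediately above the CYP3A4 line: "anticipated use of any concomitant medication during or within seven days prior to initiation of study treatment that is known to cause QT prolongation".

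Protocol 4.4 and 4.5.2 record medication, including herbal remedies and supplements, from seven days before first dose. Section 4.4.2.4 says strong and moderate CYP3A inhibitors and inducers should be avoided during cobimetinib treatment because cobimetinib is a sensitive CYP3A substrate. Section 4.4.5 bans St. John's wort over study treatment and for two weeks after it. Section 4.4.6 bans grapefruit juice over the study and for 30 days after the last dose.

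**The concern.** An exclusion based on recent exposure should bar use in the days just before first dose. Taken at its word, this one does the reverse. It bars use a week or more back, however remote, and is silent on the last six days. A patient who last drank grapefruit juice a month before dosing would breach it, while one who took St. John's wort two days before dosing would not.

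The wording matters because it is an operative eligibility rule. Protocol 9.2 does not allow eligibility waivers, and SAP 5.7.1 summarises violations of inclusion and exclusion criteria among major protocol deviations. At stake are a correct eligibility decision and some protection against an interacting agent still acting when cobimetinib starts.

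**Working it through.** No sample size, power or precision figure depends on this point. The check is a day count and a comparison of texts.

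**1. Day count.** In Appendix 2, screening runs from Day -28 to Day -1 and treatment starts on Day 1, so Day -k is k days before first dose.

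| Reading | Days excluded | Days covered of Day -7 to Day -1 |
|---|---|---|
| As written (*at least* seven days) | Day -7 and all earlier days | 1 of 7 |
| *Within* seven days | Day -7 to Day -1 | 7 of 7 |

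The two readings share only Day -7. Days left open as written: 7 - 1 = 6 (Day -6 to Day -1).

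**2. Seven-day criteria in 4.1.2.** Corticosteroid dose, acetaminophen, pregnancy test, QT drugs and CYP3A4 agents make 5. Four refer to the final week and one says *at least*.

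**3. All look-back windows in 4.1.2.**

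- Cancer-related criteria: corticosteroid dose, major surgery, acetaminophen, prior malignancy (4).
- Cardiac criteria and trauma: angina, myocardial infarction, traumatic injury (3).
- Skin exacerbation, haemorrhage, stroke or transient ischaemic attack, severe infection (4).
- Infection signs, pregnancy test, antibiotics, live vaccine, immunostimulants, immunosuppressants, investigational drug, QT drugs, CYP3A4 agents (9).

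Total: 4 + 3 + 4 + 9 = 20. Of these, 18 say *within*, 1 says *during* (corticosteroids) and 1 says *at least* (CYP3A4).

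**4. Other signs of intent.** Seven-day drug rules outside 4.1.2 also say *within*: narrow-window P-glycoprotein substrates (4.4.2.4), and torsades-risk drugs and acetaminophen (4.4.5). The medication record starts seven days before first dose, so the literal rule applies mostly to a period that is not routinely recorded. Section 4.5.1 allows re-screening after washout of a prior medication. The literal text allows no washout, because past use would exclude a patient permanently.

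**5. What other rules already close.**

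- "Treatment with therapeutic oral or IV antibiotics within two weeks prior to initiation of study treatment" and "Signs or symptoms of infection within two weeks prior to initiation of study treatment" (4.1.2) remove most patients on treatment for infection.
- Active tuberculosis and a positive HIV test are exclusions.
- In Cohort 2, anticonvulsants other than gabapentin, vigabatrin and levetiracetam are barred.
- Agents that also prolong QT or carry torsades risk meet the Cohort 2 QT criterion or the 4.4.5 rule.
- Section 4.4.2.4 tells investigators to consult prescribing information on concomitant drugs, and 4.4.2.5 advises against herbal therapies. These are cautions, not bars.
- The grapefruit ban in 4.4.6 may reach back into screening, because it runs over the study rather than over treatment.

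**6. What remains.** St. John's wort is the clearest case: its only other specific rule starts with study treatment. Prophylactic antibiotics are expressly permitted, and azoles taken without active infection could fall outside the QT and torsades rules. The documents do not show which agents in these two groups would actually escape.

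**The case against.** The strongest reply is that no site could apply the literal text. It would exclude almost anyone who had ever drunk grapefruit juice, on a history the study does not collect. A sensible site would read the line as requiring the agent to have been stopped at least seven days earlier. Apart from how Day -7 itself is treated, that is the window *within seven days prior* describes. This largely stands: most sites would probably apply a washout, and the documents show no misapplication. It also means the correction changes no intent. It does not make the sentence right, because that reading supplies a verb the criterion lacks.

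A reader might infer that this criterion is the only pre-dose protection for both of its named examples. For grapefruit juice the documents do not support that. Section 3.2 counts study length from screening of the first patient, so a ban over the study can be read to include an enrolled patient's screening period. Section 4.4.6 states no numbered pre-dose window, so this remains a competing reading.

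A reader might also take the approximately 7-fold rise in cobimetinib exposure in 4.4.2.4 as the size of the risk. It is not. It describes co-administration of itraconazole in healthy subjects, not carry-over from use that has stopped. That text also sits under cautionary, not prohibited, therapy, and for vemurafenib the same section allows strong CYP3A4 inhibitors and inducers with caution.

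Finally, the benefit may reach few patients. Section 3.2 plans about 48 months in total with at least 24 months of follow-up, implying roughly 48 - 24 = 24 months of accrual. Enrolment was under way by 9 July 2019, and Version 5.0 cites sources accessed on 28 May 2021, more than 22 months later. Accrual may have been near its end, although Section 4.1 still speaks of Cohort 2 patients to be enrolled and nothing says Cohort 2 had closed.

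**Conclusion.** The criterion is wrong as written in both places and should be corrected, but the correction is minor. The literal text covers 1 of 7 intended days and leaves 6 open. It is the only one of 20 look-back windows in 4.1.2 with this wording. That a final-week washout was meant is an inference, strongly supported by the parallel criteria, the medication look-back and the re-screening provision.

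In practice the gap is narrow: probable site interpretation and the other rules leave St. John's wort as the clearest agent without another stated pre-dose washout. A reader might infer that patients entered with interacting agents on board, or that the efficacy results are compromised. The documents support neither. They give no number of patients affected and no measure of carry-over, and nothing in the sample size or primary analysis depends on the criterion.

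**What to change.** In Protocol 4.1.2 and in the synopsis exclusion criteria, replace *at least seven days prior* with *within seven days prior*. Make the change at the next amendment, with the approvals required by Section 9.7, and apply it prospectively to patients screened under the amended text. Cohort 1 is closed to enrolment (Section 4.2), so only Cohort 2 patients still to be screened are affected.

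The cost is one phrase in two places. No new data collection is needed for drugs, herbal remedies or supplements, which are already recorded for those seven days. Foods are not in that list, so grapefruit juice would be asked about at the screening eligibility review under Section 4.5.1. No change to the SAP or to any analysis is needed.
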